10.8 Patient Withdrawal

10.8.1 *Individual Treatment Discontinuation*

The assigned study treatment might be permanently discontinued at any time by the investigator for safety or medically justified reasons.

There are several other reasons the patient may withdraw from treatment, including, but not limited to, patient withdrawal of consent to treatment, the sponsor terminating the study, or the patient being lost to follow-up. The reason for early discontinuation of treatment will be documented in the patient's medical records and the electronic case report form (eCRF). Patients who discontinue treatment early will continue to be followed through the end of the study.

10.8.2 *Participant Withdrawal from the Study*

There are several reasons the patient may withdraw from the study, including, but not limited to, patient withdrawal of consent for participation in the study, the sponsor terminating the study, or the patient being lost to follow-up. The reason for early discontinuation of treatment will be documented in the patient's medical records and the eCRF.

10.8.3 *Lost to Follow-Up*

A participant will be considered lost to follow-up if he/she fails to provide data or biologic samples after the discharge at the time points described in the protocol before the completion of the study.

The site should attempt to contact the patient (eg, by phone or last known mailing address) in order to:

- a. Determine if the patient is deceased and the reason of the death;

- b. Reschedule, if still alive, the missed hospital or home visit as soon as possible; counsel the participant on the importance of maintaining the assigned visit schedule; and ascertain whether the participant wishes to and/or should continue in the study.

Should the participant continue to be unreachable, he/she will be considered lost to follow-up.

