12.8 Handling of Missing Data

All reasonable efforts will be made to reduce the rate of missing data. Investigators will be trained about the importance of patient retention and full data capture. In addition, reasonable attempts should be made by the investigators to emphasize continued subject's participation for the full duration of the trial.

Missing data for the primary endpoint will be handled as follows:

1. In the case of death of any cause, the patient will be considered to have the worst outcome with censoring at the planned follow-up visit (Day 43).
2. In the case of patients who are hospitalized for any reason and withdraw consent, the patient will be considered to have the worst outcome with censoring at the planned follow-up visit (Day 43).
3. In the case of loss to follow-up or other reasons unrelated to COVID-19 for discontinuing the study, the data will be considered missing at random and will be censored at the last available visit if the patient does not have fecal viral RNA clearance before discontinuation from the study.

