All subject data collected at scheduled and unscheduled visits, excluding data collected in the daily diary, will be presented in individual subject data listings. Dates will be shown in subject listings as they have been recorded. Data listings will be sorted by treatment group, subject identification number, date/time and visit where applicable. The treatment group (randomized) as well as subject's sex and age will be stated on each listing where applicable. Unless otherwise stated, data listings will be based on all subjects randomized. When no data are available for a table or listing, an empty page with the title will be produced with suitable text (e.g., "There are no records for this table/listing.").

Unless otherwise specified, baseline will be defined as the last non-missing assessment prior to or on the date that the first dose of treatment is taken. For subjects who are randomized, but not treated, the baseline will be defined as the last non-missing assessment prior to or on the date of randomization. Assessments from both scheduled and unscheduled visits will be used to determine baseline. The date of first and last dose will be collected on the End of Treatment eCRF.

Study day will be calculated relative to the first dose date:

- Day 1 is defined as the first dose date
- Assessments before the first dose date: Study Day = Assessment Date – First Dose Date
- Assessments after the first dose date: Study Day = Assessment Date – First Dose Date +1

Summaries or analyses by study visit will be based on data collected at scheduled visits (i.e., nominal visits as collected on eCRF) and data from unscheduled visits will not be included. Efficacy analyses for time to viral clearance or clinical improvement will include data from both scheduled and unscheduled visits. Laboratory treatment emergent summaries will also include data from both scheduled and unscheduled visits.

A two-sided hypothesis test will be used at a significance level of 0.05 for comparison between the niclosamide and the placebo group for the primary efficacy analysis. All other statistical analyses will also be performed using a two-sided hypothesis test at a nominal significance level of 0.05. No adjustment for Type I error will be made for multiple comparisons. Models will include stratification factors, age (<65 years or ≥65 years) and sex (female or male), unless an insufficient amount of data exists where convergence or the analysis cannot be performed.

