4.1. Sample Size

The sample size for Part 1 of the study was selected empirically for an initial evaluation of safety in subjects with COVID-19.

The sample size for Part 2 of the study was determined by simulations based on the following assumptions:

- The time to fecal viral clearance has an exponential distribution for each treatment arm.
- The median time to fecal viral clearance is anticipated to be approximately 21 days for placebo arm and 10 days for niclosamide arm.
- Fecal viral clearance assessments are performed at Day 3, 7, 14, 28, 42 after first dose.
- Log-rank test (2-sided) is conducted to compare treatment difference.

Using a 1:1 randomization ratio, a sample size of 30 patients per treatment arm (60 patients total with a positive stool test for SARS-CoV-2 on Day 1) provides 74% power to detect a significant treatment difference for alpha=0.05 and 83% power for alpha=0.10. It is expected that approximately 40% of COVID-19 patients will be positive for SARS-CoV-2 in the stool sample. Therefore, approximately 150 patients with COVID-19 are needed to be enrolled/randomized to ensure 60 patients have a positive stool test for SARS-CoV-2 on Day 1.

To assess the sensitivity analysis of the above power calculation, additional scenarios of assumptions of stool positivity rate and longer time to fecal viral clearance for niclosamide arm (i.e. less treatment effect) are also evaluated in the below table.

Total Sample Size for Enrollment	Stool Positivity Rate	Niclosamide: Median Time to Fecal Clearance in Days	Placebo: Median Time to Fecal Clearance in Days	2-sided Significance Level (Alpha)	Statistical Power (%)
150	0.3	10	21	0.05	61
150	0.4	10	21	0.05	74
150	0.5	10	21	0.05	84
150	0.3	12	21	0.05	40
150	0.4	12	21	0.05	49
150	0.5	12	21	0.05	61

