8.1. Primary Efficacy Endpoint

The primary endpoint for Part 2 of the study is the time to fecal viral RNA clearance for subjects with a positive stool test for SARS-CoV-2 on Day 1 assessed by RT-qPCR in the niclosamide arm compared to the placebo arm.

Time to fecal viral RNA clearance is defined as the time (days) from the first dose of study treatment to the first stool RT-qPCR sample negative for SARS-CoV-2, after which all stool samples (if any) are negative. A stool sample is considered negative for SARS-CoV-2 if the test result is reported as “Not Detected”; otherwise, the stool sample is positive if the test result is reported as “Detected”. Furthermore, an “Inconclusive” test result is considered positive if it is followed directly by a positive test result; an “Inconclusive” test result is considered negative if it is followed directly by a negative test result. Subjects without fecal viral RNA clearance will be censored as follows:

- In the case of death of any cause, the subject will be considered to have the worst outcome with censoring at the planned Day 43 follow-up visit.
- In the case of hospitalization for any reason and withdrawal of consent, the subject will be considered to have the worse outcome with censoring at the planned Day 43 follow-up visit.
- In the case of study discontinuation prior to Day 43 follow-up visit due to any other reasons, the subject will be censored at the last available visit.
- In the case of study completion for Day 43, the subject will be censored at the date of the actual Day 43 follow-up visit.

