8.1.1. Primary Analysis

The analysis of the primary efficacy endpoint, time to fecal viral RNA clearance, will be conducted on the EE set.

The number and percentages of subjects achieving and not achieving the first fecal viral RNA clearance will be summarized up to each post-first dose study visit (Days 4, 8, 15, 22, 29, 36, and 43) by treatment group. For each study visit, only subjects with available assessment at the visit or having a negative stool test before the visit will be included in the summary and counted in the denominator for the percentages.

A stratified log-rank test will be used to compare time to fecal viral RNA clearance between niclosamide and placebo treatment groups adjusting for stratification factors, age (<65 years or ≥65 years) and sex (female or male). The two-sided p-value will be reported. The estimate of the hazard ratio (niclosamide vs. placebo) and the associated 95% confidence interval (CI) will be obtained from a Cox Proportional Hazards model adjusting for stratification factors and will also be reported.

Kaplan-Meier curves with 95% CIs will be generated for the total population by treatment group. Summary statistics obtained from Kaplan-Meier estimates, including the median time to fecal viral clearance with corresponding 95% CI and the proportion of subjects achieving fecal viral clearance at 3, 7, 14, 21, 28, 35, and 42 days post first dose (Day 1), will be summarized by treatment group.

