8.3.6. Time to nasopharyngeal viral clearance assessed by RT-PCR

Only subjects with positive test on Day 1 will be included in this analysis.

Time to nasopharyngeal viral clearance is defined as the time in days from the first dose of study treatment to the first nasopharyngeal RT-PCR sample negative for SARS-CoV-2. Subjects without nasopharyngeal clearance will be censored using the same rules as described for the primary efficacy endpoint in [Section 8.1](#).

A summary table will include the number and percentage of subjects achieving and not achieving the first nasopharyngeal viral clearance up to each post-first dose study visit (Days 4, 8, 15, 22, 29, 36, and 43) by treatment group. For each study visit, only subjects with available assessment at the visit or having a negative nasopharyngeal test before the visit will be included in the summary and counted in the denominator for the percentages.

Time to nasopharyngeal viral clearance will be analyzed using the same time to event methods as described for the analysis of the primary endpoint in [Section 8.1.1](#).

8.3.7. Proportion of subjects requiring hospitalization and duration of hospitalization from first dose through Day 43

Hospital admissions and dates of stay will be captured on the Hospitalizations eCRF.

Summary table containing the proportion of subjects requiring any hospitalization and the duration of hospitalization will be presented for each treatment group. A subject will be considered as requiring hospitalization if the subject has at least one hospital admission with an admission date between the first dose date and the Day 43 follow-up visit date (inclusive). The duration of hospitalization in days will be calculated by taking the sum of the duration (discharge date – admission date + 1) for each hospitalization.

9. Safety Analysis

Safety analyses will be conducted on safety data collected through the Day 43 follow-up visit for all randomized subjects and will be included as part of the Day 43 Final Analysis for the main CSR. All safety analyses will be performed using the SAF set and will be presented separately for Part 1 and Part 2 of the study unless otherwise specified.

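### Uncleared completers are censored at the Day 43 visit even without a late stool result, so patients who stop giving stool count as still shedding

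*SAP*

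**What the plan says.** SAP 8.1 defines the event by stool results alone: the first negative sample after which any further samples are also negative. Uncleared patients fall under four censoring rules. Two treat the patient deliberately as a worst case and censor at the planned Day 43 visit: death, and hospitalization with withdrawal of consent. For other discontinuations, "the subject will be censored at the last available visit". For everyone else, "In the case of study completion for Day 43, the subject will be censored at the date of the actual Day 43 follow-up visit". None of the four mentions the date of the last stool result.

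SAP 8.1.1 uses a different basis for its by-visit clearance table, where "only subjects with available assessment at the visit or having a negative stool test before the visit will be included in the summary". The log-rank, Cox and Kaplan-Meier analyses in the same section have no such condition. SAP 8.1.2 offers one sensitivity analysis, the same analysis in the per-protocol set. SAP 8.3.6 carries the rule to the other specimen-based endpoint: "Subjects without nasopharyngeal clearance will be censored using the same rules as described for the primary efficacy endpoint".

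Protocol 12.8 covers death, hospitalization with withdrawal, and loss to follow-up or other discontinuation; in the last case the data "will be censored at the last available visit if the patient does not have fecal viral RNA clearance before discontinuation from the study". It has no rule for a completer with missing stools. Protocol 10.8.3 describes as lost to follow-up a participant who "fails to provide data or biologic samples after the discharge", but it ends by applying that status to someone who stays unreachable. A patient who attends visits without giving stool does not clearly fall under it.

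**The concern.** Take a patient whose Day 8 stool is positive, who gives no further stool and who attends Day 43. Nothing is known about fecal shedding after Day 8, yet the patient stays in the risk set as uncleared for 43 − 8 = 35 more days. SAP section 8 says missing data are not imputed, but this has the effect of carrying the positive result forward.

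Three things are at stake:

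- The Kaplan-Meier curves understate clearance.
- The hazard ratio is pulled toward 1, and power falls in a trial planned at only 74%.
- The by-visit table drops this patient while the Kaplan-Meier estimate keeps the patient as a non-clearer, so one report could show two different Day 43 clearance figures from the same data.

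The pattern is possible under the protocol. Sections 10.7 and 10.7.3 allow remote assessment and self-collected stool at home, so attending and giving a sample are separate acts.

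**Working it through.** **Inputs.** From SAP 4.1: exponential clearance times, medians of 10 days (niclosamide) and 21 days (placebo), 30 stool-positive patients per arm, two-sided log-rank test, stated power 74% at alpha 0.05 and 83% at 0.10. From SAP section 4: primary alpha 0.05, two-sided. From SAP 8.1.1: visits 3, 7, 14, 21, 28, 35 and 42 days after first dose (the power simulation in 4.1 used only 3, 7, 14, 28 and 42). All stopping rates below are assumptions.

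**1. Reproduce the plan's figure.** Probability of clearance by day 42 is 1 − 2^(−42/10) = 94.6% on niclosamide and 1 − 2^(−42/21) = 75.0% on placebo. Expected events are 30 × (0.946 + 0.750) = 50.9. The design hazard ratio is 21/10 = 2.1. Schoenfeld's formula gives Φ(√(50.9/4) × ln 2.1 − 1.96) = Φ(0.687) = 75.4%. Simulation (40,000 trials) gives 73.5% and 83.3% on the five planning visits, and 74.5% and 83.9% on the seven scheduled visits. The stated 74% and 83% reproduce.

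**2. Compare two rules.** Each simulated trial was analysed twice with an unstratified log-rank test: uncleared patients censored at day 42 (SAP rule), or at their last stool. Power in %, seven visits, equal stopping in both arms:

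| Stool pattern | 10% affected: SAP rule / last stool | 20% affected: SAP rule / last stool |
|---|---|---|
| Permanent stop, all after Day 8 | 63.8 / 71.3 | 54.4 / 68.2 |
| Permanent stop, uniform over visits | 65.8 / 72.4 | 58.5 / 70.2 |
| Permanent stop, exponential time* | 67.2 / 72.5 | 61.2 / 70.5 |
| Permanent stop, all after Day 15 | 69.0 / 72.8 | 64.4 / 70.7 |
| Permanent stop, all after Day 29 | 73.5 / 74.0 | 73.0 / 73.1 |
| Only Day 43 stool missing | 74.3 / 74.2 | 74.1 / 73.7 |
| Each stool missed independently | 73.7 / 73.9 | 72.5 / 72.4 |

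*20,000 trials, Monte Carlo standard error about 0.35 points, 74.3% with complete stool; the other rows use 40,000 trials.

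Some loss occurs under either rule because events go unseen. In the exponential row at 20%, the total loss is 74.3 − 61.2 = 13.1 points: 74.3 − 70.5 = 3.8 is unavoidable and 70.5 − 61.2 = 9.3 comes from the censoring rule. With stopping spread over follow-up, about 3 of 60 patients are affected at 10% and 6 to 7 of 60 at 20%.

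**3. Estimates, 20% exponential stopping.**

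| Day 43 clearance | Niclosamide | Placebo | Difference |
|---|---|---|---|
| True | 94.6% | 75.0% | 19.6 |
| Kaplan-Meier, SAP rule | 87.5% | 67.8% | 19.7 |
| By-visit table, SAP 8.1.1 | 95.3% | 77.3% | 18.0 |

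The one-step log-rank hazard ratio, exp((O − E)/V), is 2.14 under the SAP rule and 2.38 with last-stool censoring. It runs above the design ratio of 2.1, so read the two values against each other. The Kaplan-Meier difference with last-stool censoring is 19.5 points.

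**4. Type I error, no true effect (median 15 days in both arms).** SAP rule: 5.1% to 5.2% with equal stopping, 6.0% to 6.5% at 20% vs 10%, 9.1% to 9.8% at 30% vs 10%. Last-stool censoring: 5.1% to 5.3% throughout. With median 21 days in both arms and 0% vs 20% stopping after Day 8, the figures are 12.0% and 5.2%.

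**5. Stopping related to clearance (base rate 20%).** If the stopping hazard triples after clearance, last-stool censoring gives 94.1%/74.0% and the SAP rule 84.8%/65.6%. If slow clearers stop four times as often, the figures are 94.7%/76.6% and 83.8%/65.9%. Against 94.6%/75.0%, last-stool censoring is within 1.6 points in both.

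**6. Stratified test.** The planned test is stratified by age and sex. In a check with 4,000 trials per cell and exponential stopping, the gap between rules went from 72.3 − 66.0 = 6.3 points unstratified to 67.2 − 62.1 = 5.1 stratified at 10% stopping, and from 69.7 − 59.8 = 9.9 to 64.8 − 56.9 = 7.9 at 20%. A 3,000-trial check with assumed strata shares of 40/40/10/10 gave 5.0 to 3.7 and 8.8 to 7.3.

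None of these simulations models visit windows, positives after a negative, or inconclusive results.

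**The case against.** The strongest reply is that the harmful pattern is undocumented. Stool is scheduled at every visit through Day 43 and can be collected at home, so nothing shows that attending patients will stop early and for good. Late or sporadic gaps barely matter. This stands, and it is why the size is conditional.

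The documents also offer partial remedies. SAP 5.2 defines major deviations broadly enough that persistent missing stool could remove a patient from the per-protocol set, but that is discretionary and affects only a supportive analysis. Protocol 10.8.3 could be read to make such a patient lost to follow-up, but its closing sentence points the other way.

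The by-visit table is descriptive, so its disagreement with Kaplan-Meier is not a formal contradiction. It is itself biased upward and would still differ slightly after the change: 95.3 − 94.6 = 0.7 and 77.2 − 75.0 = 2.2 points in one check.

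The rule is conservative when stopping is equal, and the 9% to 10% type I error needs widely unequal stopping in a blinded trial. That is fair, but the SAP reserves its deliberate worst-case censoring for death and hospitalization with withdrawal and gives no such reason for completers. With unequal stopping the rule is not conservative.

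Finally, one could keep the current rule and add last-stool censoring only as a sensitivity analysis. That would be better than the present plan, but it leaves the primary result resting on time in which no one looked.

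**Conclusion.** The concern holds. SAP 8.1 counts unobserved time as uncleared for completers without late stool, and no other provision in either document reliably corrects it. Under permanent stopping spread over follow-up, equal in both arms, the rule itself costs roughly 5 to 7 points of power at 10% stopping and 9 to 12 at 20%, somewhat less with the stratified test. It costs about 14 points (68.2 − 54.4) if 20% stop after Day 8, and about a point or less if gaps are late or sporadic. Kaplan-Meier clearance is about 7 points too low in each arm at 20% exponential stopping, while the difference between arms hardly moves. Type I error is affected only when stopping differs between arms. All stopping rates are assumed, so the actual effect is unknown. The change should be made, since the plan has little power to spare; confidence in the size is medium.

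**What to change.** - In SAP 8.1 and 8.3.6, censor uncleared patients at the collection date of their last evaluable specimen. Keep the death rule and the hospitalization-with-withdrawal rule unchanged.
- State that this assumes stopping is unrelated to clearance.
- Settle two details in the wording: a patient with no post-baseline specimen is censored at Day 1 and adds nothing to the log-rank test, and the text must say whether a final inconclusive result counts as evaluable.
- Keep Day 43 visit censoring as a sensitivity analysis.
- Report by arm the number of uncleared completers with no Day 43 stool result and the date of their last one.
- Record in SAP section 14 the departure from protocol 12.8, which censors discontinuers at the last available visit.
- Leave formed stool, abdominal symptoms and WHO score as they are; they are recorded at the visit and need no change when the Day 43 assessment is done.

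The cost is revised wording in two sections, one sensitivity analysis, one small table and one section 14 entry. No new data are needed.

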8.1.1. Primary Analysis

The analysis of the primary efficacy endpoint, time to fecal viral RNA clearance, will be conducted on the EE set.

The number and percentages of subjects achieving and not achieving the first fecal viral RNA clearance will be summarized up to each post-first dose study visit (Days 4, 8, 15, 22, 29, 36, and 43) by treatment group. For each study visit, only subjects with available assessment at the visit or having a negative stool test before the visit will be included in the summary and counted in the denominator for the percentages.

A stratified log-rank test will be used to compare time to fecal viral RNA clearance between niclosamide and placebo treatment groups adjusting for stratification factors, age (<65 years or ≥65 years) and sex (female or male). The two-sided p-value will be reported. The estimate of the hazard ratio (niclosamide vs. placebo) and the associated 95% confidence interval (CI) will be obtained from a Cox Proportional Hazards model adjusting for stratification factors and will also be reported.

Kaplan-Meier curves with 95% CIs will be generated for the total population by treatment group. Summary statistics obtained from Kaplan-Meier estimates, including the median time to fecal viral clearance with corresponding 95% CI and the proportion of subjects achieving fecal viral clearance at 3, 7, 14, 21, 28, 35, and 42 days post first dose (Day 1), will be summarized by treatment group.

